### **11.3 Deaths**

The number of subject deaths will be summarized 1) for deaths occurring within 30 days of the last dose of study drug in combination period, 2) for deaths that occurred more than

30 days of last dose of study drug in combination period, 3) for all deceased subjects. Death causes under each category will also be summarized.

#### **11.4 Analysis of Laboratory**

Subjects that do not have a baseline measurement or do not have any post-baseline measurements will not be included. Post-baseline measurements collected 30 days after last dose of study drug in combination period will not be included. Last dose here will be determined by each analysis period.

##### **Analyses of Shift from Baseline in Clinical Laboratory Data**

Where applicable, blood chemistry and hematology determinations will be categorized according to NCI CTCAE version 4.0 grades. The baseline and maximum grades are defined respectively as the baseline grade and as the highest (worst) grade during post-baseline visit on or prior to 30 days of last study drug. Section 6.0 describes the analysis convention for laboratory values used in summary of shift from baseline analyses. Baseline NCI CTCAE version 4.0 grades and maximum post-baseline grades, as well as shifts from baseline grade 0 - 2 to maximum grade 3 - 4, will be assessed by cross-tabulation for both chemistry and hematology. Shifts from baseline grade 0 - 2 to final grade 3 - 4 will be assessed by cross-tabulation for Proteinuria.

Detailed listings of all measurements collected in the extracted database for subjects experiencing NCI CTCAE Grade 3 to 4 blood chemistry and hematology values will be provided. All measurements collected, regardless of the number of days after the last dose of study drug, will be included in these listings.

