**Table 8. Study Activities in Phase 2**

Activity	SCR a	C1 D-2	D1 through D3 Combination Cycles	C1 D8	C2 Through Last Combination Cycle D1	C2 Through Last Combination Cycle D8	Monotherapy/ Veliparib/ PBO D1 of Each Cycle Starting in Maintenance	Tumor Assessments Every 6 Weeks First 30 Weeks	Tumor Assessments Every 9 Weeks Thereafter	Post-Treatment Follow-Up	Final Visit o	30-Day Follow-Up Visit p	Survival Follow-Up
Informed Consent b	X												
Medical and History c	X												
Physical Exam (including weight) d	X	X		X	X		X				X	X	
Performance Status (ECOG)	X	X			X		X				X	X	
12-Lead ECG	X										X		
Vital Signs	X	X	X C1 only	X	X		X				X	X	
Pregnancy Test Serum (s), Urine (u) e	X (s)	X (u)											
Hematology f	X	X		X	X	X	X				X	X	
Chemistry f	X	X			X		X				X	X	
Coagulation Tests	X										X		
HBsAg, HCV RNA g	X												
Urinalysis	X										X		

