#### **8.1.7.6 Analyses of Laboratory Data Using NCI CTCAE**

Where applicable, blood chemistry and hematology determinations will be categorized according to NCI CTCAE version 4.0 grades, and shifts from baseline NCI CTCAE version 4.0 grades to maximum and final post-baseline grades will be assessed. The baseline and final grades will be defined respectively as the grade of the last measurement collected prior to the first dose of study drug, and as the grade of the last post-baseline measurement collected no more than 30 days after the last dose of study drug. If multiple values are available for a post-baseline measurement, then the value with the highest NCI CTCAE grade will be used in the assessment of shift. Comparisons of the number of subjects experiencing a shift from baseline grades of 0 to 2 or no grade to maximum post-baseline grades of 3 to 4, and from baseline grades of 0 to 2 or no grade to final post-baseline grades of 3 to 4 between Arm A and Arm C as well as between Arm B and Arm C will be performed using Fisher's exact tests. Additional analyses including all measurements collected, regardless of the number of days after the last dose of study drug, will be performed.

Detailed listings of data for subjects experiencing NCI CTCAE Grade 3 to 4 blood chemistry and hematology values will be provided. All measurements collected, regardless of the number of days after the last dose of study drug, will be included in these listings.

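### SAP 11.4 tabulates the shift to final Grade 3–4 only for proteinuria, although Protocol 8.1.7.6 specifies it for blood chemistry and hematology, and the SAP gives no reason for the change

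*SAP*

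**What the plan says.** **Protocol 8.1.7.6** limits its scope to CTCAE-graded results from the two blood panels, chemistry and hematology. For these it plans that "shifts from baseline NCI CTCAE version 4.0 grades to maximum and final post-baseline grades will be assessed". It defines the final grade "as the grade of the last post-baseline measurement collected no more than 30 days after the last dose of study drug". Two events are then to be compared by Fisher's exact test, A vs C and B vs C. One is the move from a low or absent baseline grade to a maximum of Grade 3–4. The other is the move "from baseline grades of 0 to 2 or no grade to final post-baseline grades of 3 to 4".

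**SAP 11.4** repeats the same grading scope (chemistry and hematology). Its definitions stop short of a final grade: "The baseline and maximum grades are defined respectively as the baseline grade and as the highest (worst) grade during post-baseline visit". It then plans that "shifts from baseline grade 0 - 2 to maximum grade 3 - 4, will be assessed by cross-tabulation for both chemistry and hematology", and closes with "Shifts from baseline grade 0 - 2 to final grade 3 - 4 will be assessed by cross-tabulation for Proteinuria".

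**SAP 6.0** defines a general final value for laboratory variables that runs to 30 days after the last maintenance dose when maintenance was given. The opening of SAP 11.4 instead cuts laboratory data at 30 days after the last combination-period dose, then adds that the last dose depends on the analysis period. SAP 11.1 rules out between-arm safety comparisons unless specified, and 11.4 specifies none.

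**The concern.** The SAP presents itself (section 3.0) as elaborating the protocol's methods. Here it moves a protocol analysis from the two panels for which it was written to a parameter the protocol section does not cover. Protein appears under Urinalysis in Protocol Table 12, and in Phase 2 urinalysis is scheduled only at Screening and the Final Visit (Table 8). The SAP explains its change to the response-rate period in section 4.1, but says nothing about this one.

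The panels left without the analysis are the ones where it would be informative. Protocol 3.7 names myelosuppression, with nausea and vomiting, as toxicity expected to overlap with carboplatin/etoposide. Protocol 3.3.3 anticipates Grade 3 or 4 cytopenias when veliparib is combined with chemotherapy. The maximum-grade table shows how many subjects reached Grade 3–4 at any time. The final-grade table would show how many were still at Grade 3–4 at their last assessment, by arm. Only the first is planned.

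**Working it through.** The plan states no figure to reproduce, so the check sets the passages side by side.

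**1. Which shift tables does each document plan?**

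| Shift event | Panel | Protocol 8.1.7.6 | SAP 11.4 |
|---|---|---|---|
| To maximum Grade 3–4 | Chemistry | yes | yes |
| To maximum Grade 3–4 | Hematology | yes | yes |
| To final Grade 3–4 | Chemistry | yes | no |
| To final Grade 3–4 | Hematology | yes | no |
| To final Grade 3–4 | Proteinuria | not named | yes |

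Two events × two panels = 4 protocol tables. The SAP keeps 2, drops 2 and adds 1 outside the protocol section's scope.

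**2. Which comparisons?** Two events × two arm contrasts = 4 Fisher's exact tests per graded parameter in the protocol. The SAP plans none.

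**3. Which baseline category?** The protocol counts subjects with baseline Grade 0–2 or no grade. The SAP counts Grade 0–2 only.

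**4. Does another SAP output give the final grade by arm?**
- Visit-wise change from baseline (SAP 6.0) covers chemistry and hematology, but summarises values, not grades.
- Adverse-event tables (SAP 11.2) count Grade 3 or 4 events and events leading to reduction, interruption, delay or discontinuation. They do not show whether an event had resolved.
- Dose-delay counts (SAP 9.0, item 3) are given by arm for the period before maintenance. They are indirect.
- Listings (SAP 11.4) show every measurement for subjects with a Grade 3–4 chemistry or hematology value, regardless of time since last dose. They allow subject-by-subject tracing but are not a tabulation.

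None of these is a by-arm count of subjects ending at Grade 3–4.

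**5. Are the data there?** Yes. Under Table 8, Phase 2 hematology is drawn on Day 8 of Cycle 1, on Days 1 and 8 of later combination cycles, on Day 1 of maintenance cycles, at the Final Visit and at the 30-Day Follow-Up. Chemistry follows the same pattern without the Day 8 draws. Grading is already needed for the maximum-grade table.

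**6. Would final grade be unambiguous if the panels were simply swapped back?** No. Section 11.4 does not define it. SAP 6.0 extends into maintenance, while 11.4 points to the combination period. The protocol counts from the last dose of study drug and does not limit that to the combination period. The same table could give different counts under the two SAP windows.

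**The case against.** The strongest reply is that little is lost. The protocol requires neutrophil and platelet recovery before Day 1 of each cycle (5.7.2.1.1), so an unrecovered count should appear as a delay, and delays are tabulated by arm. Grade 3–4 events are tabulated, maximum shifts are tabulated, and the full listings carry no 30-day cut. No endpoint, decision rule or efficacy inference depends on this table. Most of that stands and limits the severity. It does not close the gap: delays say nothing about recovery after the last cycle, and listings are not a comparison by arm.

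Three stronger readings are tempting, and the documents do not support them.

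- *A reader might infer that persistence of cytopenias goes unreported.* The final grade is one value, the last within 30 days of the last dose. A new Grade 4 on the last draw counts the same as an unresolved one, and the result depends on where in the cycle the subject stopped. It is a proxy for non-recovery, and the listings still show the course in each subject.
- *A reader might infer that the proteinuria table is worthless and should go, because many Final Visit samples would miss the window.* That depends on which of the two SAP windows applies, which is unsettled, and it would not measure the lost hematology information in any case. Protocol 3.4 lists renal toxicity for carboplatin and 8.1.7.5 plans urinalysis summaries, so a urine-protein table is not without a basis.
- *A reader might infer that the sentence was carried over from another study's plan*, since SAP 3.0 cites protocol M14-359 for Study M14-361. That is possible, but nothing in the documents establishes it.

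**Conclusion.** The concern holds as a mismatch between the two documents. SAP 11.4 assigns the final-grade shift to proteinuria alone, Protocol 8.1.7.6 specifies it for blood chemistry and hematology, and no reason is recorded. The loss is two of the four protocol shift tables, together with all of the protocol's Fisher's exact comparisons on shifts. The affected information stays available from listings and indirectly from the delay and adverse-event tables. This should be corrected, but it does not threaten the trial's conclusions. The verdict rests on the text alone and needs no assumption about event rates or visit timing. If the sponsor intended the change, the defect reduces to an undocumented departure from the protocol.

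**What to change.** In SAP 11.4:

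1. State that shifts from baseline Grade 0–2 or no grade to final Grade 3–4 will be cross-tabulated by arm for both chemistry and hematology, as in Protocol 8.1.7.6.
2. State which final value applies: the SAP 6.0 definition, which extends into maintenance, or the combination-period limit in 11.4.
3. Either carry over the Fisher's exact comparisons (A vs C, B vs C) or record their omission as a change from the protocol, with a reason.
4. Keep the proteinuria shift only as a justified addition, not as a replacement.

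If dropping the final-grade table was deliberate, say so and give the reason, as the SAP does for the response-rate period. The cost is a few sentences and one further cross-tabulation from data already collected and graded. SAP 12.0 describes unblinding as still to come, so the change should be made before then.

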#### **12.0 Timing of Efficacy Analyses and Safety Evaluations**

The model-based prediction estimated Sep. 14th, 2018 as the date of 126 PFS events across the three arms. To operationalize the data acquisition and cleaning efforts in a timely manner, all efficacy and safety data through Sep. 14th, 2018 will be retrieved and entered into the clinical database prior to breaking the study blind. When the data

collection is completed and reviewed for completeness and all data management quality assurance (QA) and quality control (QC) procedures are performed, the study blind will be broken and clinical database data will be extracted for documentation and statistical analyses of the efficacy and safety data.

### **14.1.1 Introduction**

AbbVie Study M14-361 is a Phase 1, open-label, dose escalation/Phase 2 randomized double-blind clinical trial of veliparib in combination with carboplatin and etoposide and maintenance veliparib monotherapy. Subjects enrolled in the Phase 2 portion will be randomized in a 1:1:1 ratio to the following three treatment arms:

- Arm A: veliparib + carboplatin and etoposide followed by veliparib monotherapy;
- Arm B: veliparib + carboplatin and etoposide followed by placebo monotherapy; and
- Arm C: placebo + carboplatin and etoposide followed by placebo monotherapy.

A safety Data Monitoring Committee (DMC) will be set up for the Phase 2 portion of the study to review the aggregate unblinded safety data.

#### **Phase 2 portion of the study:**

Primary Objective of the DMC:

To evaluate the safety of veliparib in combination with carboplatin and etoposide followed by veliparib maintenance monotherapy.

This DMC Agreement defines the roles and responsibilities of the DMC, including its membership, scope, timing of meetings, and communication plan.

### **14.1.2 Membership**

#### **14.1.2.1 Members**

The DMC consists of a Senior Medical Director who will serve as the Chair, as well as an Associate Medical Director and a Statistician who will serve as DMC members. No

DMC members will be from the Study Team responsible for conduct of the AbbVie Study M14-361.

The DMC members will review unblinded aggregate safety data by treatment group. In general, these data will not be shared outside the DMC. However, if deemed necessary by the DMC, ALB members (excluding any who are also Study Team members) may be asked to review the unblinded results with the DMC and these unblinded data can be shared with ALB members (excluding any who are also Study Team members) to support critical program needs. ALB members who are also Clinical Strategy Team members will not share any reviewed results with non-ALB Clinical Strategy Team members until study completion.

#### **14.1.2.2 Duration of Membership**

DMC membership will extend from the initiation of the Phase 2 portion of the study through completion of the trial. If a DMC member leaves the committee, a replacement will be selected by the TA MD/SD.

#### **14.1.3 Role of the DMC**

The DMC will provide an independent internal review and assessment of the unblinded aggregate safety data from AbbVie Study M14-361. The primary role of the DMC is to make a recommendation to the AbbVie Contact based on the unblinded analysis of available interim safety data.

The DMC will not evaluate efficacy data such as Progression Free Survival (PFS) and Overall Survival (OS). However, the incidence (rate) of subject death is considered a safety endpoint. A significant imbalance in death rate favoring the control arm (ARM C) may require action.

During the conduct of the study, the medical and safety team will monitor blinded subject laboratory results and serious adverse event data on a real-time basis. The TA MD/SD will also review blinded aggregate safety data on a regular basis and may enlist the assistance of the DMC at any time to evaluate any identified safety trend. The timeframe for trend analysis will be defined by the TA MD/SD in consultation with the DMC Chair on a case-by-case basis, depending on the nature of the safety signal.

#### **14.1.3.1 Safety Monitoring Guidelines**

The following safety data recorded in the clinical trial database will be reviewed overall and between treatment arms:

- Subject disposition;
- Dose intensity and dose reduction/interruption summary for study drug (veliparib);
- Treatment-emergent adverse events (AEs);
- AEs/SAEs relationship to study drug (veliparib);
- Treatment-emergent serious adverse events (SAEs);
- AEs leading to dose reduction/interruption of study drug (veliparib);
- Discontinuation of study drug (veliparib) due to AEs not related to disease progression;
- AEs leading to dose reduction/interruption of chemotherapy;
- Rates of death; and
- Laboratory data.

#### **14.1.4 ORGANIZATIONAL FLOW**

The DMC statistician member will be responsible for providing the unblinded analysis of the safety data required by the DMC. When the data collection and cleaning is completed for interim analysis, the clinical database will be extracted (versioned) for statistical analysis at least 10 business days prior to a scheduled DMC meeting. The DMC statistician will receive access to the necessary randomization information and statistical programs needed to generate unblinded information (tables, figures and listings) at least 7 business days prior to a scheduled DMC meeting. In turn, the DMC statistician will communicate the unblinded information to other DMC members through use of a private, limited-access SharePoint folder approximately 5 business days prior to the scheduled DMC meeting.

#### **14.1.5 MEETINGS**

##### **14.1.5.1 Organizational Meeting**

The first meeting of the DMC will be an organizational meeting. Attendees will include, but may not be limited to, the DMC members and the appropriate representatives from the Clinical Strategy Team, including the TA MD/SD, as well as Study Team members. This meeting will formally establish the DMC, thoroughly acquaint the DMC with the protocol and the DMC Agreement, and review the analysis plan for interim safety monitoring.

##### **14.1.5.2 DMC Review Meetings**

The initial DMC review meeting is planned to occur once the first 30 Phase 2 subjects complete combination treatment. Based on this initial safety DMC review, the frequency of subsequent safety DMC review meetings will be determined.

The initial safety DMC review may occur sooner than planned if the observed rate of dose-limiting toxicity (DLT)-like events in the aggregate blinded safety review of the first 15 Phase 2 subjects exceeds the rate observed in the Maximum Tolerated Dose/Recommended Phase 2 Dose (MTD/RPTD) cohort from the Phase 1 portion of the study by more than 10%. If that occurs, the DMC will convene as soon as possible to

review the aggregate unblinded safety data. A minimum of one Medical Director DMC member and the DMC statistician will have to be present to review the unblinded safety data if an immediate DMC meeting is called and other members cannot attend in the required timeframe.

The DMC Chair may request additional meetings as needed for safety reasons only.

#### **14.1.5.2.1 Open Session**

The open session attendees will include, but may not be limited to, the DMC members and the appropriate representatives from the Clinical Strategy Team, including the TA MD/SD, as well as Study Team members. The study statistician will produce and distribute Open reports to the Open Session attendees. Open reports will include tables to summarize subject accountability (number of subjects randomized, treated, discontinued and ongoing, demographic characteristics, reasons for study discontinuation and adverse event summaries). These Open reports will be aggregated across treatment arms. No unblinded information will be provided in the Open reports.

During the Open Session, the TA MD/SD and/or Clinical Scientist will provide a general update on the study and any relevant new information regarding the product under investigation, including any relevant recent literature. The TA MD/SD and/or Clinical Scientist will review the Open report with the DMC. The Study M14-361 study team can attend Open Sessions.

#### **14.1.5.2.2 Closed Session**

The DMC statistician member will provide the unblinded analysis results of the safety data as indicated in the safety monitoring guidelines (Section 14.1.3.1) to the meeting attendee's approximately 5 business days prior to the scheduled review meeting. Closed Sessions in which unblinded safety data are reviewed will be restricted to DMC members, however, the DMC may invite additional AbbVie subject matter experts (SMEs) to attend the closed sessions if the DMC determines they need to consult with AbbVie personnel

having expertise not represented on the DMC. If an SME is asked to join the closed session, the SME must not be participating in the Veliparib program.

#### **14.1.6 Communication**

The DMC members are to treat all communications regarding this clinical study, including reports, data, review meeting discussions, teleconferences, and meeting minutes, as confidential material.

A private, limited-access SharePoint folder will be created to facilitate communication between DMC members. The DMC will not share the study results with external parties or to the non-ALB Clinical Strategy Team members/Study Team until study completion; only the DMC recommendation may be disseminated, as applicable.

##### **14.1.6.1 Meeting minutes**

The DMC Chair or a designated member of the DMC will prepare meeting minutes for both the open and closed sessions. Draft open session minutes will be distributed to the meeting attendees for review within one week of the meeting. Draft closed session minutes will be distributed to DMC members only, within one week of the meeting. Formal open and closed session minutes will be available within one month following the meeting(s). The DMC Chair or designee is responsible for archiving the recommendations, the meeting materials, and minutes in the private, limited-access SharePoint folder.

The Study Project Manager will be responsible for documenting the outcome of each meeting in the trial master file at the end of the study (after the study has been unblinded).

##### **14.1.6.2 Recommendations**

After completing its review, the DMC may recommend to:

- Continue the trial without modification;
- Continue the trial with modification(s);

- Suspend opinion pending additional analyses;\*
- Terminate the trial due to safety-related concerns;
- Other action with justification\*\*

\* *The study statistician will generate any additional requested blinded analyses. The DMC statistician will generate any additional requested unblinded analyses.*

\*\* *For example, communication of findings to Investigators and/or IRB/EC if there is urgency beyond what is achievable with a protocol amendment.*

The Project Leader for veliparib will serve as the AbbVie Contact for this study. The DMC will provide a completed recommendation form (see Appendix 14.1.7) to the AbbVie Contact via email immediately after the completion of the closed session.

The AbbVie Contact will have the responsibility for reviewing and communicating with the veliparib ALB in order to decide whether to accept, modify or reject the DMC recommendation. If the DMC recommendation is to continue the trial without modification, then the AbbVie Contact should communicate this information to the Study M14-361 study team directly.

If the DMC recommendation is to (a) terminate the trial due to safety-related concerns or (b) continue the study with modification(s) (e.g.,: implement "major" unplanned changes to the study protocol), the AbbVie Contact will communicate the DMC recommendation to the veliparib ALB within 24 hours, who will make a final decision regarding the necessary action to be taken based on the DMC recommendation. The ALB meeting must include [name] as an ad-hoc member to represent Data and Statistical Sciences (DSS). If the ALB determination is to either (a) accept with modification or (b) reject the DMC's recommendation, the ALB should meet with the DMC to review this decision. The ALB may need to review the same unblinded information that was made available to the DMC when they formulated their recommendation. The ALB decision will be communicated to the Study M14-361 study team, who will be responsible for executing the directive from the ALB. Affected members of the veliparib ADT and CST will be notified of this decision in a timely manner.

